The Coaching-CRAFT intervention is meant to be a combination of CIC's coaching strategy combined with the didactic material in the recently developed web-based CRAFT intervention, VA-CRAFT [17]. The VA-CRAFT course for substance misuse has 8 modules that follow the original CRAFT intervention [9] (see Appendix 2 for module details): 1) Introduction to CRAFT, 2) Overview of CRAFT, 3) Getting Started with CRAFT: Safety Planning, 4) Understanding substance abuse, 5)

How to respond to substance abuse, 6) How to rebuild your life together, 7) How to help someone consider treatment, 8) Wrapping up. The goals of the intervention include understanding triggers and long-term reinforcement of substance misuse, ignoring unhealthy behaviors and rewarding healthy behaviors, getting support, and how to help the CSO caller help the Veteran enter treatment.

The PI will work with the Key Personnel to discuss the following factors: 1) format of the manual, 2) level of manual detail, 3) optimal pace of work with the CSO using the web-based CRAFT content, 4) optimal number and length of calls, 5) points of individualizing the material in CRAFT to the CSO's specific situation, and 6) the coach's role in identifying appropriate programs and facilitating entry into treatment soon after the Veteran indicates his or her readiness. *The group will meet by conference call regarding these factors, the PI will draft the manual, and the Key Personnel will meet again to discuss the draft. This iterative process will continue until we have a suitable draft manual. We will then seek feedback from volunteer Veterans and their family members at the CPL Michael J Crescenz VA Medical Center (Philadelphia). This feedback will be incorporated and the draft will be discussed again by the Key Personnel and the PI will produce a final draft for the trial.* We will also develop a fidelity scale for the essential targets for the telephone interventionist of Coaching-CRAFT. The manual development will occur in months 1-4.

Clinical Trial

Sample and recruitment procedures

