Recruitment for the sample in the trial will occur within the regular workflow of the CIC call center. We have estimated that on a yearly basis approximately 600 callers to CIC are first degree relatives of an OEF-OIF-OND Veteran who has a primary difficulty with substance misuse, yielding 300 potential referrals for the 6 active recruitment months of the trial. Initial assessment and problem identification has typically been conducted by a CIC call responder in the first 1-3 calls, often involving consultation with a licensed supervisor. Potential participants include the following: 1) CSO is a sibling, spouse/ intimate partner, or parent of a US military Veteran who served in Iraq or Afghanistan since 2001, 2) by the report of the CSO the Veteran of interest has a substance abuse problem that has led to interpersonal, legal, occupational, and/or health related negative consequences, 3) the CSO reports that the Veteran is not currently receiving treatment for this problem, and 4) the CSO has contact 4+times/week and lives with or within 30 min. of the Veteran. Exclusion criteria include: 1) CSO has an SUD (Form 90, see Measures), 2) the Veteran is currently incarcerated, 3) the CSO has no computer or other device with Internet access able to view video content, and 4) the CSO or Veteran likely has a psychotic disorder (CSO report on the MINI) (see Measures). Potential participants will be presented the option of being involved in the research trial, and if interested, will be contacted by the research staff. If the CSO is interested after hearing more details the research staff will conduct the additional screening, consent procedures, and baseline assessment. *We will also engage Veterans in the study at two points. First, if/when the CSO indicates that the Veteran wants treatment, we will offer help to the Veteran in an initial telephone conversation. In this conversation we will ask to use their responses as research data. Second, we will ask the CSO at 12 months after the baseline to invite the Veteran to participate (see below).*

Measures.

Demographic information (from CSO). Age, gender, race, marital status, relationship of CSO to the Veteran, living status (i.e., with the Veteran), hours in contact per week, Veteran's military service details (branch, highest rank, combat deployments, National Guard/Reserve component vs. regular Army/Navy/Marines/Air Force), Veteran's age, race, marital status, and number of children.

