Intervention acceptability, satisfaction, and engagement. We will measure satisfaction with the intervention using questions used currently by the CIC call center which asks the caller’s expectations of service, helpfulness, changes in hopefulness, and report of the Veterans desire for and engagement in care (see Appendix 2). Additional open-ended questions will assess how the telephone-based support or VA-CRAFT content could be changed to improve convenience, acceptability, or effectiveness. *We also plan to secure a HIPAA waiver to obtain VHA administrative data to verify the CSO’s report of the Veteran’s engagement in VHA care (see Human Subjects).*

We will assess the engagement of the CSO in the intervention by tracking the number and length of telephone calls with the interventionist, and the number of sessions the CSO logs in to use the web-based CRAFT material, *repeat visits to sessions*, and the degree of completion of each of the modules. Drop-outs from the intervention and drop-outs from assessment follow-up will also be carefully tracked. Drop-outs will be defined as no response after 3 attempts over 1 month.

Schedule of Assessments

Measure (source: domain)	Baseline	6 months	12 months
CSO: CSO’s alcohol & substance misuse, Veterans alcohol & substance misuse	Form 90	Form 90	Form 90
Treatment utilization	Form 90	Form 90	Form 90
Burden	Caregiver Burden Scale	Caregiver Burden Scale	Caregiver Burden Scale
CSO Symptoms, CSO perceptions of Veteran’s PTSD symptoms	MINI, PHQ-9, PCL- 5 (family ver.)	MINI, PHQ-9, PCL- 5 (family ver.)	MINI, PHQ-9, PCL- 5 (family ver.)
CSO perceptions of intervention			Open-ended questions
Web-host tracking: Engagement in interventions			Website use (time on sessions, repeat visits to sessions, completion)
Veteran: Vet’s subst. abuse & Treatment			Form 90
Veteran symptoms			MINI, PCL 5, PHQ-9
Veteran perceptions of interaction with CSO			Open-ended questions
Veteran’s MH/SA treatment engagement	Questions about treatment engagement, if/when the Veteran agrees to treatment		VHA administrative data

Trial procedures

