The primary goal of the trial intervention will be a test of the feasibility of Coaching-CRAFT, CSO’s experience and engagement in the intervention, and within-subject estimates of changes in Veterans’ engagement in treatment. We will seek to enter 50 family member callers into a nonrandomized trial over 6 months. Each research-based telephone contact will be audio recorded for examination using the fidelity scale developed in months 1-4.

An additional goal is to compare the outcome in the trial to a usual-care sample of at least 50 CIC callers that have not been offered Coaching-CRAFT, matched on the basis of the Veteran’s primary substance use problem(s), relationship of CSO to Veteran, contact time and co-habiting

status, Veteran age and gender, and race. We will select comparison cases from a several year time-frame to ensure an appropriate comparison.

The length of the active coaching of the CSO using the web-based CRAFT material is anticipated to last no longer than 6 months, but this will be determined by the treatment manual development phase. Additional assessments will occur at 6 and 12 months after study entry and will include the measures as detailed in the table (above). *At 12 months, we will ask the CSO to invite the Veteran to engage in the study and answer study questions about their symptoms, treatment, and the CSO's approach to them.* We will carefully assess the safety and risk to the CSO-Veteran relationship prior to making the decision to pursue this assessment. Working with the CSO, we will ask the CSO to ask the Veteran to be involved, including type of discussion between CSO and Veteran might be helpful, and ask the CSO to ask the Veteran to call the study staff (see Human Subjects).

Timeline

We anticipate the trial will begin in Year 1 with initial recruitment occurring from months 5-10. The trial will end in Year 2, month 22. Analyses of feasibility, satisfaction and treatment engagement will occur in months 19-24. After the formal participation in the trial, any caller who needs additional support or treatment referral will be referred to the CIC call center.

Data Analysis, Sample Size considerations, and intervention modification

Feasibility Outcomes

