We will examine CSOs ratings of the intervention with a criterion of at least 80% of those rating the intervention as helpful, leading to increased hopefulness and preparedness to help the Veteran, and that the intervention had helped the family overall. We will also examine the degree to which the subjective symptoms of distress (PHQ-9, subjective burden), decline over the Baseline, 6 month, and 12 month assessments, using a mixed methods model test of within-subjects change over time. We will compare the completion rates of the Coaching-CRAFT sample of CSOs with a sample of CSOs from the CIC QA data. "Completion" will mean at least 6 months of telephone coaching of 8+ calls. We will match CSOs receiving Coaching-CRAFT with the treatment as usual data (see above).

Intervention comparisons

In a key analysis we will also plan to test the proportion of the Veterans of the CSOs who entered treatment for substance misuse against the matched CSOs from the CIC QA data. We will use an intent-to-treat approach. Those CSOs lost to follow-up will be deemed intervention failures regarding the Veterans' engagement in treatment. We plan to use a basic test of difference between proportions in independent samples (a two sample z-test). To detect a difference between the rate of engagement in treatment using CIC QA data (i.e., 41%) and conservative outcomes drawn from the CRAFT RCTs (67%), the sample group needed to detect a difference with power of 80% in post-intervention treatment engagement outcomes, is $N = 45$, for each group [29]. Our intent-to-treat sample size of $N = 50$ exceeds this number.

Review of CSO and Veteran report: *Qualitative and treatment engagement reports*

We plan to conduct a systematic review of the responses to the post-intervention open-ended questions in order to modify the intervention as needed in preparation for a large RCT. In addition, we plan to assess the rate of Veteran inclusion in the study at 12 months, *the CSO report, the VHA report of Veteran treatment utilization, and the comparison of these different data sources.*

Considerations of alternative approaches

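### The completion rate scores coaching that ended because the Veteran entered treatment the same as disengagement, so the comparison with QA callers cannot separate early success from attrition

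*Combined protocol and SAP*

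**What the plan says.** All references are to the combined protocol and SAP.

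- **Feasibility Outcomes** (data analysis section): completion "will mean at least 6 months of telephone coaching of 8+ calls". The use of the rate is also stated: "We will compare the completion rates of the Coaching-CRAFT sample of CSOs with a sample of CSOs from the CIC QA data".
- **Intervention comparisons**: the key analysis will "test the proportion of the Veterans of the CSOs who entered treatment for substance misuse" against matched CSOs from the QA data. The planning rates are 67% for Coaching-CRAFT and 41% for CIC.
- **Intervention and manual development process**: the goals include "how to help the CSO caller help the Veteran enter treatment", and the coach's role, to be worked out in the manual, includes "facilitating entry into treatment soon after the Veteran indicates his or her readiness".
- **Sample and recruitment procedures**: a CSO is eligible only if "the CSO reports that the Veteran is not currently receiving treatment for this problem". The Veteran is offered help whenever he or she wants treatment; no month is fixed for this.
- **Measures, on acceptability, satisfaction and engagement**: "Drop-outs will be defined as no response after 3 attempts over 1 month".
- **Trial procedures**: active coaching "is anticipated to last no longer than 6 months, but this will be determined by the treatment manual development phase".

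No section says how a CSO is classified when coaching ends because the Veteran has entered treatment. No section says whether coaching stops or goes on after entry.

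**The concern.** The programme exists to get an untreated Veteran into care, and that can happen at any time. The QA results under Preliminary Studies describe a rise in engagement within roughly three months of the first call, about half the completion threshold. Take a CSO whose Veteran enters treatment in month 2 after four calls and who then sees no need to go on. The key analysis counts this CSO as a success. The completion rate counts the same CSO as a failure, no different from one who gave up. The drop-out definition does not help: it covers non-response only, so this CSO is neither a drop-out nor a completer.

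Feasibility is named first in the primary goal under Trial procedures, and the results are meant to shape the intervention before a large RCT. Completion is one of two comparisons with QA callers in the data analysis section. A report of better engagement but worse completion could lead to needless changes to the intervention if the second finding partly reflected the first.

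**Working it through.** **The plan's own figures.** The documents give no expected completion rate, so there is none to reproduce. The only sample size is 45 per group for 67% against 41% at 80% power. With a pooled-variance z-test and one-sided α = 0.05:

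n = [1.645 × √(2 × 0.54 × 0.46) + 0.842 × √(0.41 × 0.59 + 0.67 × 0.33)]² / 0.26² = 44.4, rounded up to 45.

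Two-sided α = 0.05 gives 57. The plan does not state sidedness. That is a separate matter, and nothing below depends on it; only the two rates are carried forward.

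**Inputs**

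- p = treatment entry: 0.67 and 0.41 (Intervention comparisons).
- s = share of CSOs with treatment entry who stop before 6 months or 8 calls because the Veteran is in care. Not in the documents; assumed equal in both samples.
- c = completion among all other CSOs. Not in the documents; assumed equal in both samples.

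**Formula.** Completion as defined = c × (1 − s × p). The Coaching-CRAFT deficit is therefore c × s × (0.67 − 0.41) = 0.26 × s × c.

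| s | c = 0.60 | c = 0.80 | c = 1 |
|---|---|---|---|
| 0 | 0 | 0 | 0 |
| 25% | 3.9 | 5.2 | 6.5 |
| 50% | 7.8 | 10.4 | 13.0 |
| 75% | 11.7 | 15.6 | 19.5 |

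Entries are percentage points. The last column is a ceiling: it supposes that every early-stopping entrant would otherwise have completed.

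**What a single rate hides (s = 50%, c = 0.80)**

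| | Coaching-CRAFT | CIC QA |
|---|---|---|
| Met the threshold, c(1 − sp) | 53.2% | 63.6% |
| Stopped because the goal was reached, sp | 33.5% | 20.5% |
| Other early ending, (1 − c)(1 − sp) | 13.3% | 15.9% |

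The stated rate shows a 10.4-point deficit although retention is identical by construction. Counting goal-reached stops as completed gives 86.7% against 84.1%, which reverses the sign (+2.6 points).

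**How easily the deficit is cancelled.** Break-even needs Coaching-CRAFT retention to be (1 − 0.41s)/(1 − 0.67s) times the CIC value: 1.08 at s = 25%, 1.20 at s = 50%, 1.39 at s = 75%.

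**Would early ending without treatment entry be a cleaner measure?** No. Suppose 80% retention in both samples, stopping unrelated to entry, and entry always before stopping. That category is then 0.20 × 0.33 = 6.6% for Coaching-CRAFT and 0.20 × 0.59 = 11.8% for CIC. This is a 5.2-point advantage with identical retention.

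**The case against.** The strongest objection is that the mechanism is assumed. No section says that CSOs leave, or that coaching stops, when the Veteran enters care. The course also covers safety, rewarding healthy behaviour, support and rebuilding a shared life, and the plan follows CSO distress and burden, so a CSO may have reason to continue. The number and length of calls are left to a manual not yet written. This stands: if coaching continues after entry, s is near zero and so is the deficit.

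A reader might infer that completion must run against engagement, so that a more effective programme will look less feasible. The documents do not support that. Usual CIC coaching ranges from one call to more than 20, so usual-care completion may be low for unrelated reasons, and modestly better retention under Coaching-CRAFT would cancel the effect. There is also a link in the other direction: CSOs lost to follow-up are scored as engagement failures, which ties retention positively to the key outcome.

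A reader might also take 7, 13 and 20 points as the expected size. They are the ceiling at c = 1. Moreover, 67% and 41% are post-intervention engagement rates, not rates of entry before month 6 or call 8, so s has to absorb the timing.

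Finally, call counts, module completion and drop-outs are tracked separately in the trial sample, and no test, threshold or go/no-go rule is attached to completion; the 80% criterion concerns CSO ratings. A fixed-dose measure is a legitimate description of exposure. All of this is true and limits the consequence to interpretation. It does not repair the comparison, because the drop-out definition does not enter the completion rate and no matching classification of QA callers is described.

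**Conclusion.** The point holds as a gap in the outcome definition. As written, the completion rate puts early success and disengagement in one class, and no other section separates them. Whether this distorts the comparison, and which way the observed difference goes, cannot be settled from the documents. The deficit of 0.26 × s × c requires s above zero and similar in both samples, with equal underlying retention. Under those assumptions and c = 0.80, it is about 5 to 16 points for s from 25% to 75%.

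A reader might conclude that feasibility should rest on early endings without treatment entry instead. That does not follow: that category also depends on treatment entry, in the direction that favours the more effective programme. Neither measure is safe alone.

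A related inconsistency is textual and needs no assumption. Trial procedures expects coaching to last at most six months, while completion requires at least six. The expected maximum is thus the required minimum, and any earlier ending fails whatever its reason.

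**What to change.** Keep the stated completion rate. Add to Feasibility Outcomes that, in both the Coaching-CRAFT and the QA sample, each CSO will be placed in one of three categories, reported side by side:

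- (a) met the 6-month and 8-call threshold;
- (b) coaching ended earlier, with the Veteran already in substance-misuse treatment;
- (c) coaching ended earlier, without treatment entry.

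State that no feasibility conclusion will rest on (a) or (c) alone. Reconcile the coaching length in Trial procedures with the minimum in Feasibility Outcomes.

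The cost is a sentence or two in the analysis section. For trial CSOs, the planned call tracking, Form 90 and VHA administrative data should supply what is needed. The downside lies in the comparator: QA records may hold treatment status only at follow-up and not the date of entry, so (b) may be approximate there, and the report should say so. Category (b) also records status, not motive, so it will include some CSOs who left for other reasons after the Veteran had entered care.

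### The key comparison with QA callers sets no common starting point or outcome window for treatment entry, and does not limit comparators to Veterans out of treatment at the start

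*Combined protocol and SAP*

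**What the plan says.** All references are to the combined protocol and SAP.

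- **Endpoint and test.** Under Intervention comparisons, the plan will "test the proportion of the Veterans of the CSOs who entered treatment for substance misuse against the matched CSOs from the CIC QA data", using a two-sample z-test of proportions. The only timing is in the power statement, "with power of 80% in post-intervention treatment engagement outcomes". On missing outcomes it says: "Those CSOs lost to follow-up will be deemed intervention failures".
- **Trial timing.** Under Trial procedures, coaching "is anticipated to last no longer than 6 months", with its length left to manual development, and "Additional assessments will occur at 6 and 12 months after study entry". In the Schedule of Assessments, treatment utilization by Form 90 is collected at both times and VHA data only at 12 months. The call center's own questions include the concerned significant other's (CSO's) "report of the Veterans desire for and engagement in care", but the schedule gives them no month.
- **Comparators.** "We will select comparison cases from a several year time-frame". Matching is on the Veteran's primary substance problem, "relationship of CSO to Veteran, contact time and co-habiting" status, and Veteran age, gender and race.
- **Eligibility.** Under Sample and recruitment procedures, the Veteran must not be receiving treatment for the problem, by CSO report. Enrolment comes after the initial call-center assessment, which typically takes one to three calls.
- **QA data.** The call center section of Preliminary Studies mentions engagement within about 3 months of first call. It then gives counts in care: 248 rising to 382 of 939 callers without substance misuse, and 35 rising to 49 of 109 with it. No window is stated for the 109.

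**The concern.** Entry into treatment accumulates with time. If one group is read at 6 or 12 months and the other at about 3, the proportions can differ with no effect of the intervention. Baseline status adds a second problem. A trial Veteran can count only by newly entering treatment, but a comparator already in care at the first call may be counted as engaged.

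The plan settles neither matter. Its timing word, post-intervention, does not choose between the two trial visits, and QA callers, who had from one call to more than 20, have no fixed end of coaching. The conclusion could therefore turn on which trial visit is used, how old the QA record is, and whether Veterans already in care are kept. The plan calls this a key analysis and justifies its sample size by it.

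**Working it through.** **1. The plan's own figures.** The 41% control rate equals 382/939 = 40.7%. That is a proportion in care at follow-up among callers without substance misuse, and 248 of the 939 (26.4%) were in care at the start. The substance-misuse counterpart is 49/109 = 45.0%, with 35/109 = 32.1% in care at the start. The planned 45 per group for 41% against 67% at 80% power is reproduced by the pooled z-test formula at one-sided 5% (44.4, rounded up to 45). At two-sided 5% the formula gives 57. The plan states neither alpha nor sidedness; two-sided 5% is assumed below.

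**2. Usual-care entry rate.** Not in care at the start: 109 - 35 = 74. Net new: 49 - 35 = 14. So p = 14/74 = 18.9%. This is a net figure, because exits from care are not reported.

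**3. Effect of the window alone.** Assume no intervention effect, comparators limited to Veterans not in care, 50 per group, and p as a 3-month rate. Let f be the later entry rate relative to the early one; f is an assumption, ranged from 0 to 1. The expected trial rate is 1 - (1 - p)^(1 + f) at 6 months and 1 - (1 - p)^(1 + 3f) at 12 months. The last two columns give the exact binomial probability that the pooled z exceeds 1.96 in favour of Coaching-CRAFT.

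| f | Trial rate, 6 mo | Trial rate, 12 mo | Favours Coaching-CRAFT, 6 mo | Favours Coaching-CRAFT, 12 mo |
|---|---|---|---|---|
| 0 | 18.9% | 18.9% | 2.6% | 2.6% |
| 0.1 | 20.6% | 23.9% | 4% | 9% |
| 0.25 | 23.1% | 30.7% | 7% | 28% |
| 0.5 | 27.0% | 40.8% | 16% | 68% |
| 1 | 34.3% | 56.8% | 42% | 98% |

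If p is instead a 6-month rate, a 6-month trial outcome gives 2.6% (no inflation). A 12-month outcome gives 3-42%, since the window doubles as in the 6-month column.

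**4. Loss counted as failure.** Assume 20% of trial outcomes are lost, so the trial rate is multiplied by 0.8, and f is 0.25 to 1. The 3-month QA case then gives 2-17% at 6 months and 10-82% at 12 months. With 20% lost in both groups it gives 7-33% and 22-93%.

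**5. Effect of baseline status alone.** Take equal windows, no effect and a trial rate of 18.9%. If comparators are counted by being in care, the test favours usual care 68% of the time against 41% and 81% against 45.0%. If only new entries count but Veterans already in care stay in the denominator, the comparator rate is 14/109 = 12.8%, and the test favours Coaching-CRAFT 14% of the time. The direction depends on the counting rule.

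**The case against.** **The timing is less open than it looks.** The document's other uses of post-intervention lean to 12 months. The open-ended questions given that label are scheduled only then, the Veteran assessment described as following the intervention is at 12 months, and the VHA data sit there too. Recruitment in months 5-10 puts 12-month visits in months 17-22, compatible with analysis in months 19-24. This stands as evidence of intent, but none of it is tied to the key comparison. A 12-month reading against a 3-month QA record would also be the widest mismatch.

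**QA records may reach 6 months.** Under Feasibility Outcomes, completion is compared with QA callers and means at least 6 months of coaching with 8 or more calls. That implies some QA records run that long. A reader might infer that no QA follow-up beyond 3 months exists; the document does not support that. Completion concerns coaching, however, so it does not set the month at which engagement is read.

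**The figures rest on assumed entry rates.** They do. With little entry after 3 months the error rate is near nominal, and the ranges are not estimates.

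**Veterans already in care have not entered treatment, so the endpoint wording excludes them.** This is a fair reading. Yet the planning rate of 41% is an in-care proportion, and no rule removes such Veterans from the comparators.

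**It is a feasibility study.** The alternative-approaches section puts proof of concept ahead of efficacy, and Trial procedures calls this comparison an additional goal. That limits the severity. The actual timing of QA engagement questions may also be set out in the call-center manuals or Appendix 2, which are not available here.

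**Conclusion.** The point holds: the key comparison lacks a common starting point, a common window and a rule on baseline treatment status. Followed as written, it can compare new entry over 6 or 12 months with prevalence in care over some other period. It should be fixed before recruitment.

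The size is illustrative. With a 3-month QA window, the chance of a false finding for Coaching-CRAFT is 3-42% at 6 months or 3-98% at 12 months, against 2.6% with equal windows. It is not inflated if both groups are read at 6 months. Counting Veterans already in care favours usual care 68-81% of the time. These figures assume no effect, 50 per group, a two-sided 5% test, and 14/74 as the entry rate with exits unknown.

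A reader might infer that the plan is biased towards Coaching-CRAFT. The documents do not support that: the two problems can pull in opposite directions and the net is unknown. Nor can the November 2014 start date be used to give the 109 callers a long follow-up. It is attached to the 939 callers without substance misuse, and the 109 are a separate subsample.

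**What to change.** Under Intervention comparisons, state the following.

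- **Outcome.** New entry into substance-use treatment, by CSO report, within one window of the same length in both groups, among Veterans reported not in substance-use treatment at the index point.
- **Window.** Six months if QA engagement was recorded then. Otherwise use the QA window, with trial treatment-start dates asked at the existing 6-month contact. Report other trial time points as within-group description only.
- **Index point.** As nearly as possible the same event in both groups, for example completion of the initial call-center assessment. Trial CSOs then pass through screening, consent and baseline, and a Veteran who enters treatment in that gap becomes ineligible. So exclude comparators whose Veteran entered treatment within an equal lag, set at the typical trial enrolment lag. Both groups are then out of treatment when counting starts.
- **Missing outcomes.** CSOs without an outcome count as not engaged in both groups.

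**Cost.** Plan wording and possibly one start-date question; no extra contacts. Limiting comparators to Veterans not in care keeps about 74/109 = 68%, so about 50/0.679 = 74 otherwise matched callers are needed to yield 50, and the lag exclusion may remove a few more. It also needs entry dates in the QA records. Start dates rely on CSO recall, and a 3-month outcome would be read while coaching may still be under way.

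### The 80% power claim uses an undiluted 67% engagement rate although lost CSOs are scored as failures, so the 5 CSOs above 45 are not a cushion against loss

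*Combined protocol and SAP*

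**What the plan says.** All the elements of the calculation stand in one paragraph, Intervention comparisons, within the data analysis and sample size section. The test is a two-sample z-test of independent proportions. The assumed engagement rates are 41% for usual Coaching Into Care (CIC), from quality assurance (QA) data, and 67% for Coaching-CRAFT, described as a conservative figure from the CRAFT trials. For "power of 80% in post-intervention treatment engagement outcomes" the number required "is $N = 45$, for each group". The analysis is by intention to treat, and "Those CSOs lost to follow-up will be deemed intervention failures" as regards the Veteran's engagement. The paragraph closes with "Our intent-to-treat sample size of $N = 50$ exceeds this number".

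The Measures section shows that loss is expected and will be tracked: "Drop-outs will be defined as no response after 3 attempts over 1 month". No expected loss rate is given anywhere. Trial procedures sets assessments at 6 and 12 months and a comparison sample of 50 or more. Neither alpha nor sidedness is stated.

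**The concern.** Having 50 where 45 are needed protects against loss only if lost CSOs leave the analysis. Then 5 losses per group would leave 45 and 45, and power would still be 80.5%. The plan's rule works differently: a lost CSO stays in the denominator and scores zero. Loss then shrinks the difference between the groups instead of the sample size, and a few extra CSOs do little to offset that. The sample size uses 67% with no reduction, so the closing sentence offers a reassurance that does not follow from the rule earlier in the paragraph.

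What is at stake is how the comparison is read. The plan calls it a key analysis and attaches a formal power figure to it. A non-significant result would be weighed against a belief in 80% power that the design may not have.

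**Working it through.** **Inputs.** From Intervention comparisons: p1 = 0.41, p2 = 0.67, power 80%, two-sample z-test, 45 required, 50 planned. From Trial procedures: a comparison group of at least 50, taken here as 50. Alpha and sidedness are assumptions.

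**Step 1: reproduce 45.** With pooled variance under the null and unpooled under the alternative,

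n = [z_α √(2 p̄(1−p̄)) + z_β √(p1(1−p1) + p2(1−p2))]² / (p2−p1)², with p̄ = 0.54.

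One-sided 5%: [1.645 √0.4968 + 0.842 √0.4630]² / 0.26² = 44.4, so 45, the plan's figure. Two-sided 5% gives 56.5, so 57. The plan's number thus implies one-sided 5% (equivalently two-sided 10%). The one-sided unpooled form gives 43.

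**Step 2: carry the failure rule.** Suppose 67% is the rate among followed CSOs and loss is unrelated to outcome. With k of 50 lost, the tested rate is 0.67 × (50 − k)/50, still over 50. Then

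power = Φ[(p2 − p1 − z_α s0)/s1],

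where s0 and s1 are the standard errors of the difference under the null (pooled) and the alternative (unpooled).

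- k = 0: (0.26 − 1.645 × 0.0997)/0.0962 = 0.998, power 84.1%.
- k = 1: p2 = 0.657, power 80.3%.
- k = 2: p2 = 0.643, power 76.1%.
- k = 5: p2 = 0.603; (0.193 − 1.645 × 0.1000)/0.0981 = 0.291, power 61.4%.
- k = 10: p2 = 0.536, power 35.0%.

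**Step 3: both readings of the rule, both conventions.** Power with 50 per group:

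| Loss | One-sided 5%, Coaching-CRAFT only | One-sided 5%, both groups | Two-sided 5%, Coaching-CRAFT only | Two-sided 5%, both groups |
|---|---|---|---|---|
| 0% | 84% | 84% | 75% | 75% |
| 5% | 74% | 80% | 62% | 70% |
| 10% | 61% | 76% | 49% | 65% |
| 20% | 35% | 68% | 24% | 56% |

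For both groups, p1 is multiplied by (1 − loss) as well. With 2 lost per group, one-sided power is 81.1%; with 3 it is 79.5%.

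**Step 4: size needed for 80% power, one-sided 5%.** If only Coaching-CRAFT is diluted: 60 per group at 5% loss, 82 at 10%, 194 at 20%. If both are: 50, 56 and 70.

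**Step 5: sensitivity to the form of the test.** With the unpooled statistic, one-sided power is 85.5%, 81.7% and 77.5% for 0, 1 and 2 lost. Exact binomial power of the pooled test is 83.0%, 79.3% and 75.1%.

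**The case against.** The strongest reply is that the size of the effect rests on choices that the documents leave open.

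- **What 67% includes.** If the CRAFT trials behind it already counted lost CSOs as failures, and loss here is similar, there is no further dilution. The documents do not say. This stands as a condition on every figure above.
- **Loss unrelated to outcome.** If 67% is the rate in the whole group and the Veterans of lost CSOs would have engaged at half that rate, each loss removes less. The tested rate is 0.67 − 0.335 × k/50, and power is 80.3% with 2 lost and 73.9% with 5. This stands too.
- **Which groups the rule covers.** Speaking of intervention failures, and drawing the comparison from existing QA data, favour applying it to Coaching-CRAFT only, but the text does not settle it.
- **More comparators.** The plan sets a minimum of 50. With 100 and only Coaching-CRAFT diluted, one-sided power is 86.1% at 2 lost and 82.1% at 3, though 72.5% at 5. Extra comparators reduce the problem without removing it.
- **A pilot.** Trial procedures makes feasibility the primary goal, and the section on alternative approaches puts proof of concept ahead of efficacy. This limits the impact.

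A reader might infer a fixed rule that 80% power holds as long as no more than 1 of 50 CSOs is lost. The documents do not support that. It is false at two-sided 5%, where power is below 80% with nobody lost; it shifts if both groups are diluted; and it fails with 100 comparators. A reader might also infer that power fails at any ordinary 12-month loss, or that 45 is miscalculated. No attrition figure is given, the outcome is called post-intervention without being tied to 12 months, and 45 reproduces exactly.

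**Conclusion.** Wrong as written: the plan states a power that the design does not deliver under its own loss rule, unless 67% already contains comparable losses. The fault is an omitted loss assumption, not a slip in computing 45.

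At 10% loss with 50 per group, and on the assumptions of Step 2, power is below 80% whichever groups the rule covers, even on the one-sided convention that favours the plan. If only Coaching-CRAFT is diluted, the shortfall is already there at 5% loss; if both groups are, 5% loss still leaves 80%.

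The consequence is moderate. It concerns the interpretation of one comparison in a feasibility study, although one that the plan singles out as key.

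**What to change.** Keep 50. Rewrite the power statement so that it gives:

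1. alpha and sidedness;
2. whether 67% already counts CSOs lost to follow-up as failures;
3. whether the failure rule covers Coaching-CRAFT only or both groups;
4. the size of the comparison group;
5. power at 0, 5, 10 and 20% loss under those choices, in place of the remark that 50 is more than 45.

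Do not write in a fixed number of tolerable losses, since it would hold under only one combination of these choices.

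The cost is one paragraph and a small table. No extra participants are needed, and neither the test nor the failure rule changes. The drawback is that the stated power will probably look less favourable.
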